### 10.1.3 Subgroup Analyses

Descriptive summary statistics of the primary effectiveness outcome will be provided in the following subgroups:

- Race (Asian, other)
- Lens status of study eye (phakic, pseudophakic)
- History of trabeculectomy (yes, no)
- Prior glaucoma procedures (with incisional or cilioablative procedure, without incisional or cilioablative procedure, no)
- Baseline IOP  $\geq 20$  mm Hg and  $\leq 35$  mm

A forest plot will be provided to summarize all subgroup analyses results.

## 10.2 SECONDARY EFFECTIVENESS ASSESSMENTS

The mean and 2-sided 95% CI for raw Hour 0 IOP and the corresponding change from baseline Hour 0 IOP will be estimated using mixed-effects model for repeat measures (MMRM) at Month 1, 3, 6, 8, 10, and 12 with visit as a fixed effect and baseline Hour 0 IOP as a covariate. An unstructured covariance matrix will be used for repeated measures on the same patient; if the model with unstructured covariance fails to converge, an alternative covariance structure will be chosen. MIXED procedure available in SAS software will be used to fit the MMRM model; see sample SAS code below:

[figure not shown]
```
proc mixed data=one(where=(visit gt 0)) method=reml;  
  class visit pid;  
  model respvar=bliop visit/ddfm=kr;  
  repeated visit/subject=pid type=un;  
  lsmeans visit/cl alpha=0.05;  
  ods output lsmeans=lsms(keep=visit estimate lower upper);  
run;
```

The variable ‘respvar’ represents the Hour 0 IOP or corresponding change from baseline as applicable. Other variables are same as those described in Section 10.1. The least squares means and 95% CIs for Months 1, 3, 6, 8, 10 and 12 will be tabulated. In fitting the above model, missing data will not be imputed.

[figure not shown]
The number of IOP-lowering medications taken and corresponding change from baseline will be summarized by visit with descriptive statistics and 2-sided 95% CI for the mean. The change from baseline in the number of IOP-lowering medications taken will also be summarized by visit and the following categories:  $\geq 3$  medications reductions, 2 medications reductions, 1 medication reduction, no change, 1 medication increase, 2 medications increase, and  $\geq 3$  medications increase.

Mean (SE) Hour 0 IOP will be plotted overtime without missing data imputation and mean number of IOP-lowering medications taken will be displayed by visit in the plot.

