4.1 Structure

This is a prospective, multicenter, single-arm, open-label clinical trial designed to demonstrate the safety and IOP-lowering effectiveness of XEN. Following completion of all required preoperative examinations, and if the patient meets the study criteria, XEN will be unilaterally implanted. Approximately 65 patients will be enrolled at up to approximately 15 clinical sites to be unilaterally implanted with XEN and followed for up to 12 months postoperatively.

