8.3.2 Secondary Effectiveness Analyses

The mean and 2-sided 95% CI for raw IOP with the corresponding change from baseline will be estimated using mixed effect model repeat measurement including all post-baseline visits with visit and baseline IOP as fixed effects with data from Months 1, 3, 6, 8, 10, and 12. An unstructured covariance matrix will be used for repeated measures on the same patient; if the model with unstructured covariance fails to converge, an alternative covariance structure will be chosen. Additionally, the number of IOP-lowering medications will be summarized by visit with descriptive statistics (mean, standard deviation, minimum, maximum) and 2-sided 95% CI for the mean. The secondary effectiveness analyses will be performed using the implanted population.

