### **10.0 EFFECTIVENESS ANALYSES**

The primary effectiveness measure is based on IOP measurements at post-baseline visits and number of IOP-lowering medications taken during post-baseline visits (see section 16.1 for more details). Any IOP measurements collected following non-study surgical procedures for IOP control or device explant (i.e., device failures) will be excluded from the analyses. Any medications taken following non-study surgical procedures for IOP

control will be excluded when determining the number of IOP-lowering medications. A look-up table of MedDRA terms to identify non-study surgical procedures for IOP control will be provided by the study MSP.

No formal statistical hypothesis will be tested.

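### The 95% CI for mean IOP change comes from LS means at a baseline mean treated as fixed; in this single-arm trial it is somewhat too narrow as a population interval

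*SAP*

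**What the plan says.** Protocol 4.1 describes the design: "This is a prospective, multicenter, single-arm, open-label clinical trial designed to demonstrate the safety and IOP-lowering effectiveness of XEN". For the secondary endpoint, SAP 10.2 states: "The mean and 2-sided 95% CI for raw Hour 0 IOP and the corresponding change from baseline Hour 0 IOP will be estimated". The model is an MMRM "with visit as a fixed effect and baseline Hour 0 IOP as a covariate". The sample code fits post-baseline visits only, with "model respvar=bliop visit/ddfm=kr" and an unstructured covariance. It takes the mean and interval from "lsmeans visit/cl alpha=0.05", once with raw IOP as the response and once with change. Protocol 8.3.2 gives the same model, "with visit and baseline IOP as fixed effects with data from Months 1, 3, 6, 8, 10, and 12".

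Neither document says that the interval is conditional on this sample's baseline mean. The visible text has no unadjusted interval for IOP change. SAP 10.0 adds "No formal statistical hypothesis will be tested", so the interval is the whole of the inference on mean IOP change.

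**The concern.** With no option to set the covariate, LSMEANS evaluates each visit mean at the observed average of `bliop` and treats that average as a known constant. The Kenward-Roger option corrects for estimated covariance parameters, not for this. In a two-arm contrast the baseline mean largely cancels. Here the single-arm mean is itself the reported result, so its uncertainty should include the sampling variation of baseline.

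The plan's own code shows the omission. Raw IOP and change differ only by a covariate already in the model, so the two fits have the same residuals and give the same CI width. Intervals for a population mean IOP and a population mean change would not in general be equally wide. At stake is overstated precision for a secondary result.

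**Working it through.** **The plan's own figure.** The documents give no precision for the IOP-change interval. The only stated precision is ±0.145 for the primary proportion with 50 patients. It reproduces: the exact Clopper-Pearson interval at 25/50 is 0.355 to 0.645, half-width 0.1447. The present point does not touch it.

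**Formula.** Let follow-up IOP be Y = a + bB + e, with B the baseline and n patients. With complete data the LS mean of change at the observed mean baseline equals the sample mean change.

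- Variance the model reports, for raw IOP and for change alike: Var(e)/n
- Variance of the mean change over repeated samples of patients: [Var(e) + (1−b)² Var(B)]/n
- The same for raw IOP: [Var(e) + b² Var(B)]/n
- SE ratio for change: R = √{Var(e) / [Var(e) + (1−b)² Var(B)]}; coverage ≈ 2Φ(1.96R) − 1

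**Inputs.** Protocol 2.1 reports for the earlier US study a baseline SD of 3.7, a mean reduction of 6.4 with SEM 1.1 (95% CI 4.2 to 8.7), and n = 52 at Month 12. That n is printed beside medication use, so applying it to IOP is an assumption. It gives an SD of change of 1.1 × √52 = 7.93. The slope b is not in the documents and is varied.

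**Case 1: SD of change 7.93, baseline SD 3.7.** Here R = √[1 − (1−b)² × 13.69/62.9]. The full half-width is 1.96 × 1.1 = 2.16 mm Hg.

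| b | R | Coverage | Printed half-width | Shortfall (mm Hg) |
|---|---|---|---|---|
| 0 | 0.885 | 91.7% | 1.91 | 0.25 |
| 0.25 | 0.937 | 93.4% | 2.02 | 0.14 |
| 0.5 | 0.972 | 94.3% | 2.10 | 0.06 |
| 0.75 | 0.993 | 94.8% | 2.14 | 0.01 |
| 1 | 1.000 | 95.0% | 2.16 | 0 |

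If n was 65, the SD of change is 1.1 × √65 = 8.87 and coverage runs from 92.5% (b = 0) to 95.0% (b = 1).

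**Case 2: tighter follow-up IOP, assumed SD 4, baseline SD 3.7, n = 65.** Here Var(e) = 16 − b² × 13.69.

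| b | R | Coverage | Half-width printed / full (mm Hg) |
|---|---|---|---|
| 0 | 0.734 | 85.0% | 0.97 / 1.32 |
| 0.25 | 0.814 | 88.9% | 0.95 / 1.16 |
| 0.5 | 0.887 | 91.8% | 0.86 / 0.97 |

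**Raw IOP.** The omitted term is driven by b, so this interval is worst when b is near 1. With an assumed follow-up SD of 8 and baseline SD 3.7, coverage is 95.0% at b = 0, 94.3% at b = 0.5 and 91.8% at b = 1.

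**Simulation of the six-visit model.** Settings: common slope, unstructured covariance, 65 patients with 15 lost, baseline SD 3.7, 1,000 runs per setting (Monte Carlo error about 0.7 to 1 point), and a t quantile on n − 2 df in place of Kenward-Roger.

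- Follow-up SD 4, b = 0.25: mean model SE 0.516 against an empirical SD of 0.629. Coverage of the population mean change was 89.3% as planned and 94.6% with the omitted term added. The planned interval covered the conditional mean 93.8% of the time, which points to the omitted term as the cause.
- Follow-up SD 8, b = 0.25: 94.3% as planned, 95.5% with the term.
- Follow-up SD 4, b = 1: 94.9% and 95.0%.

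**The case against.** The best defence is that the interval is not wrong for its own target. It is valid for the mean at the observed mean baseline, baseline-adjusted MMRM LS means are conventional, SAP 10.2 calls the tabulated quantities least squares means, and the objective speaks of up to 65 patients with ACG. That would suffice if the SAP named the conditional target. It does not: the section opens by promising the mean and its CI without qualification.

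The objection on size largely stands. A reader might infer from Case 2 that the interval is badly off, with coverage in the mid-80s. The documents do not support that as the expected result. Case 2's SDs of change for b = 0 to 0.5 are 5.45 to 4.00, which at n = 52 means an SEM of 0.76 to 0.55, against the 1.1 that Protocol 2.1 reports. Case 1 is nearer the documents. If the cited SEM was itself model-based, it may already omit the baseline term, and 7.9 would then be a residual SD.

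It also stands that no performance goal or test uses the interval and that the three secondary variables are unranked. SAP 10.2 plots mean (SE) Hour 0 IOP, an unadjusted SE for raw IOP but not for change. The text of SAP 10.3 is not visible and cannot be counted either way.

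**Conclusion.** The point holds with modest size. The planned intervals are valid conditional on the observed mean baseline. As intervals for population means they leave out the sampling variation of baseline. For change, the error is always towards overstated precision, and it vanishes only if b = 1. Entry requires an IOP of at least 20 mm Hg, and regression to the mean makes b = 1 unlikely.

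On the only relevant figure in the documents, coverage is about 92% to 95% and the half-width is 0 to 0.25 mm Hg short, beside a mean reduction of 6.4 in that study. This rests on n = 52 for the SEM, on borrowing the earlier study's SDs, and on b between 0 and 1. Coverage of about 85% to 92% is possible only if follow-up IOP proves much tighter (SD 4, b from 0 to 0.5). A reader might also infer that the effectiveness conclusion is undermined. It is not: only a secondary interval is affected.

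**What to change.** Make baseline a response. The SAP's dataset already codes it as visit 0, so drop the filter that removes it, drop `bliop`, and fit `model iop=visit / ddfm=kr; repeated visit / subject=pid type=un;`. Report the visit means and the visit-minus-baseline contrasts with their 95% CIs. Baseline still informs missing visits through the covariance. With complete data the contrast is the paired mean change, whose interval kept 95% coverage in simulation; the full seven-visit model was not itself simulated. Record the change in SAP 17.0 as a departure from Protocol 8.3.2.

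A lighter alternative keeps the planned model and adds to the squared SE the term (b̂ − 1)² s²_B / n for change, or b̂² s²_B / n for raw IOP. Here b̂ is the baseline slope in the raw-IOP fit and s_B the sample SD of baseline.

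The cost is SAP text, a few lines of SAS and a slightly wider interval. The first option also needs a 7×7 rather than 6×6 unstructured matrix (28 rather than 21 parameters), with 65 patients implanted and at least 50 expected at Month 12.

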## 10.3 OTHER EFFECTIVENESS ASSESSMENTS

## **11.0            SAFETY ANALYSES**

The safety analysis will be performed using the Implanted Population. Safety assessments include adverse events (AEs), XEN procedure and assessments, pregnancy test, and ocular parameters as determined through assessments of visual acuity, visual field, pachymetry, biomicroscopic slit lamp, gonioscopy, and ophthalmoscopic examinations.

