6.1.3.2 Postoperative Management

6.1.3.2.1 Hypotony

Investigators must monitor patients for clinically significant findings related to hypotony, such as shallow anterior chamber, persistent choroidal effusions, hypotony maculopathy, and

vision loss. Investigators will use their best medical judgment to manage hypotony, including reformation of the anterior chamber. Cycloplegic medications may be used for patients, as needed, during the initial healing phase or in phakic eyes. If used, medications must be recorded on the eCRF.

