8.3.3 Other Effectiveness Analyses

8.3.4 Safety Analyses

Safety analyses will be performed using the implanted population. The number and percentage of patients reporting AEs will be tabulated regardless of causality. AEs, adverse device effects (ADEs), BCVA, line change in BCVA from baseline, biomicroscopic slit lamp, and ophthalmoscopy findings will be summarized by frequencies at each visit.

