### 11.2.1 XEN Surgical Assessment

- XEN procedure (XEN implant only, XEN and other procedures). Further breakdown the other procedures (Cataract extraction/phacoemulsification, Clear lens extraction, Goniosynechialysis, Iridoplasty, other)
- Target Quadrant location (Superior, Nasal, Inferior, Temporal)
- Antifibrotic used (Mitomycin, Other)
- Number of sclera channels (1, 2, ..., 6)
- XEN freely mobile under the conjunctiva (yes, no)
- Additional surgical maneuvers (yes, no)
- Post-implantation bleeding (yes, no)
- Bleb formation (yes, no)
- Surgical complications (yes, no). If yes, further breakdown by complication (Detached Descemet's membrane, Iris damage, Lens contact, Vitreous bulge or loss, Significant AC bleeding, Retrobulbar hemorrhage, Conjunctival perforation, Shallow anterior chamber with peripheral iridocorneal touch, Flat anterior chamber with peripheral iridocorneal touch extending to the pupil, Other)

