  - Cells
  - Flare
  - Anterior Synechiae
  - Hypopyon
  - Hyphema
  - Other

Number and percent of patients in each of the above sub-categories will be presented using the worst severity observed in the SE by visit.

**Ophthalmoscopy Exam:** These exams will be performed at Screening, Baseline, Months 1, 3, 6 and 12/Early Exit. At each of these exams, any findings noted (yes, no, not

evaluable) in the ‘Vitreous’, ‘Optic Nerve Exam’, ‘Fundus Exam’, ‘Macula’, and ‘Retina Periphery’ will be recorded.

Number and percent of patients with findings noted in the above areas in the SE will be summarized by visit. Further, following data will also be collected associated with each of the above categories.

Vitreous: Severity (+0.5, +1, +2, +3, +4, not evaluable) associated with each finding: ‘Cells’, ‘Vitreous Haze’, ‘Vitreous Hemorrhage’, ‘Posterior Vitreous Detachment’ and ‘Other’. These data associated with the SE will be summarized in number and percent of patients format by visit.

Optic Nerve: ‘Disc Hemorrhage’ and ‘Other Disc Pathology’. Number and percent of patients with findings in each of these two areas in the SE will be summarized by visit.

In addition, Optic Nerve-Cup/Disc ratio data (numerical) of the SE will also be summarized by visit.

**Lens Status and Opacification**: Lens status findings questionnaire will be administered at screening, baseline, Months 1, 3, 6 and 12/Early Exit. Lens status at each assessment will be recorded as ‘Phakic’, ‘Pseudophakic’ or ‘Aphakic’. Lens status of the SE will be summarized by visit.

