### **16.0 DATA HANDLING CONVENTIONS**

#### **16.1 VISIT TIME WINDOWS**

Table 16.1–1 presents the analysis visits assigned for efficacy and safety analyses and the corresponding range in Study days (window) during which an actual visit may occur.

Table 16.1–1. Visit Time Windows

Analysis Visit	Target Visit Daya	Window
Baseline	Day 1	Days $\leq 1$
Day 2	Day 2	Days [2, 4]
Day 8	Day 8	Days [5, 11]
Week 2	Day 15	Days [12, 22]
Month 1	Day 31	Days [23, 61]
Month 3	Day 92	Days [62, 137]

Month 6	Day 183	Days [138, 213]
Month 8	Day 244	Days [214, 274]
Month 10	Day 305	Days [275, 335]
Month 12	Day 366	Days $\geq$ 336

a Relative to the date of the XEN implant. Day 1 = the date of the XEN implant. There is no Day 0 or Week 0.

If an assessment date (if the assessment date is unavailable, use visit date instead) is on or after the date of XEN implant, the study day is calculated using (Assessment date – date of the XEN implant + 1). If the assessment date is before the date of the XEN implant, the study day is calculated using (Assessment date – date of XEN implant). Therefore, a negative day indicates a day prior to XEN implant date.

For multiple scheduled or unscheduled visits falling within the same analysis visit window, the assessment closest to the target visit day will be used for by visit summaries. If two visits are equally close to the target visit day, the later visit will be used as analysis visit.

For by visit and severity summaries, the results with maximum severity for the visit should be chosen if multiple scheduled or unscheduled visits falling within the same analysis visit window.

For number of IOP-lowering medications taken during post-baseline visits, analysis visits for IOP measurements will be derived first. Post-baseline analysis visit days of IOP measurements will then be compared to start and stop date of each concomitant IOP-lowering medication record to determine number of IOP-lowering medications taken during post-baseline visits.

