## **16.2 REPEATED OR UNSCHEDULED ASSESSMENTS OF SAFETY PARAMETERS**

Following unscheduled assessments are allowed: Pregnancy test, IOP assessment, Manifest refraction, Gonioscopy, Pachymetry, BCVA and Visual field exam.

IOP assessment done at unscheduled visits for safety purpose will not be included in efficacy analysis of IOP.

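### No visible safety analysis uses measured IOP, so early hypotony is counted only when it is reported as an adverse event or leads to explant

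*SAP*

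**What the plan says.** **The duty.** Protocol 6.1.3.2.1: "Investigators must monitor patients for clinically significant findings related to hypotony, such as shallow anterior chamber, persistent choroidal effusions, hypotony maculopathy", and vision loss. The only IOP level attached to hypotony is in Protocol 4.4.1.1, which uses 6 mm Hg as the point below which medication may be cut back.

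**The data.** The visit schedule (Protocol Table 1-1, SAP Table 4-1) has study-eye IOP and slit lamp at Day 2, Day 8, Week 2 and every later visit. Scheduled BCVA and ophthalmoscopy resume only at Month 1.

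**The safety analyses.** Besides adverse events, procedure data and pregnancy tests, SAP 11.0 covers "ocular parameters as determined through assessments of visual acuity, visual field, pachymetry, biomicroscopic slit lamp, gonioscopy, and ophthalmoscopic examinations". Protocol 8.3.4 covers adverse events and adverse device effects, and then "BCVA, line change in BCVA from baseline, biomicroscopic slit lamp, and ophthalmoscopy findings will be summarized by frequencies at each visit". SAP 11.3 has no IOP entry.

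**The IOP analyses.** The repeated-measures model in SAP 10.2 tabulates Months 1, 3, 6, 8, 10 and 12. The same section adds: "Mean (SE) Hour 0 IOP will be plotted overtime without missing data imputation". SAP 16.2 says: "IOP assessment done at unscheduled visits for safety purpose will not be included in efficacy analysis of IOP". It names no safety analysis that would take those readings.

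**Shallow chamber.** SAP 11.2.1 names "Shallow anterior chamber with peripheral iridocorneal touch, Flat anterior chamber with peripheral iridocorneal touch extending to the pupil" as surgical complications. The by-visit slit-lamp items for the anterior chamber in SAP 11.3 are cells, flare, anterior synechiae, hypopyon, hyphema and a residual 'Other'.

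**The concern.** Low pressure soon after surgery is a known risk of this device. Protocol 2.1 reports that hypotony and needling were the most frequent ocular adverse events in the earlier refractory-glaucoma study. Protocol 2.2 names flat chamber, shallow chamber and choroidal effusion as possible narrow-angle complications. The SAP calls this study pivotal, and safety is half of its objective.

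The trial measures the pressure that defines hypotony, but the visible plan does not turn those measurements into a rate. The rate will depend on whether each investigator, at about 15 sites, regards a given reading as an adverse event. Protocol Section 11 gives no IOP level for that decision. A reader of the final report could not tell an absence of low pressures from an absence of reports.

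The primary endpoint adds to this. It rewards a fall in IOP without a floor, and no visible table shows how many responders had a pressure that the protocol itself calls hypotony.

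**Working it through.** **1. The plan's own interval method.** SAP 14.0 gives a precision of ±0.145 for 50 patients (95% Clopper-Pearson). The widest interval is at 25/50: 0.355 to 0.645, half-width (0.645 − 0.355)/2 = 0.145. The figure is reproduced, and the same method is used below.

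**2. Readings outside the tabulated model.** 65 implanted eyes × 3 early visits = 195 scheduled readings if none is missed, plus any unscheduled safety readings.

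**3. Where a low early pressure could appear in the visible text.**
- Tabulated IOP model (SAP 10.2): no, it starts at Month 1.
- Plot of means (SAP 10.2): the early visits may be plotted, but a mean does not count low eyes.
- Default descriptive statistics (SAP 4.2): if applied by visit, the minimum could show that at least one eye was low, but not how many.
- IOP categories (SAP 8.2): screening and baseline only, from below 20 to above 35 mm Hg.
- Ocular adverse events by preferred term (SAP 11.1): yes, if reported.
- Reasons for stopping study treatment (SAP 7.0): yes, if persistent hypotony led to explant.
- Macula, fundus and BCVA tables (SAP 11.3): consequences only, with scheduled examinations from Month 1.

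**4. Timing.** Month 1 has target Day 31 (SAP 16.1) and a visit window of ±5 days, so the visit is planned for Days 26 to 36. In the earlier study 13 of 16 hypotony cases arose on Day 1 and resolved by Day 27 (Protocol 2.1). If the pattern repeats, most such cases would be over at or before the first tabulated IOP estimate. How that study numbered its days is not stated.

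**5. Responder rule.** SAP 10.1.1 codes success for a change of −20% or lower on the same or fewer medications. Eligible baselines are 20 to 35 mm Hg. At exactly 6 mm Hg:
- baseline 20: (20 − 6)/20 = 70.0% fall
- baseline 35: (35 − 6)/35 = 82.9% fall

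Below 6 mm Hg the fall is larger still, so the IOP part of the rule is always met.

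**6. What the missing count could say (n = 65, exact 95% CI).**
- 0 eyes: upper limit 1 − 0.025^(1/65) = 5.5%
- 13 eyes: 20.0% (11.1% to 31.8%)
- 16 eyes: 24.6% (14.8% to 36.9%)

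The last two borrow the earlier study's 13 and 16 cases among 65 subjects. They assume one case per subject and that the rates carry over to angle closure. They illustrate precision and do not predict the result.

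**The case against.** The strongest reply is that the protocol asks for monitoring of clinical findings, not for a count of a pressure value, and that those findings have reporting routes. Protocol 11.1.1 makes untoward clinical signs adverse events. Protocol Section 11 names choroidal effusion, hypotony maculopathy and flat or shallow chamber among the events that may occur. SAP 11.1 tabulates ocular events by preferred term and severity, with listings. Macula, fundus, BCVA and explant tables add to this. All of that stands: hypotony reporting is not absent. What is missing is a count based on measurement.

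It is also true that the bodies of SAP 10.3 and Protocol 8.3.3 are not visible, that table specifications sit in a separate document, and that Protocol 8.2.3 need not be an exhaustive list. SAP 16.2 places IOP under a heading about safety parameters, and the early visits have analysis windows. So it cannot be said that early or unscheduled IOP enters no table at all, only that no visible text provides one.

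Two stronger readings are tempting and are not supported:
- A reader might infer that sites will under-report hypotony, treating the earlier study's 13 Day 1 cases as raw low readings of which only some would become adverse events. Protocol 2.1 describes those cases among adverse events. They show that such reporting did pick up early hypotony, and neither document gives a reporting fraction.
- A reader might infer that a worse unscheduled acuity is always lost from the BCVA tables. SAP 16.1 says "the assessment closest to the target visit day will be used for by visit summaries", for scheduled and unscheduled visits alike, so a worse value is kept when it lies nearest the target day.

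**Conclusion.** The point holds as a gap in the visible safety analyses and calls for a cheap improvement. It is not a fault in the primary analysis. No visible safety analysis uses measured IOP. Up to 195 scheduled early readings lie outside the tabulated model, and unscheduled safety IOP has no stated safety use. Hypotony is counted only through adverse event reports made without a stated IOP level, or through explant, with indirect cover elsewhere. Postoperative shallow or flat chamber has no slit-lamp item of its own.

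The responder rule would class an eye below 6 mm Hg at Months 1 to 12 as a success if medication had not increased. The number of such eyes may be small: the 13 early cases in the earlier study had resolved by Day 27. Explanted patients are withdrawn, and readings after explant are excluded.

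The conclusion assumes that the unseen text and table shells contain no low-IOP count. If they do, the SAP should still state the threshold, denominator and choice of reading. The documents report no visual harm from the earlier hypotony cases and say that none needed surgical intervention. That is why this ranks as an improvement and not as a condition for going ahead.

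**What to change.** **Add to SAP 11.3**
- Hypotony table: number and percent of study eyes with IOP below 6 mm Hg at Day 2, Day 8, Week 2 and each later visit. Use the lowest reading in the analysis window, scheduled or unscheduled, with eyes that have a reading as the denominator.
- In the same table: eyes below 6 mm Hg at any reading from Day 2 to the end of the Month 1 window (Day 61), as a percentage of the Implanted Population with an exact 95% CI.
- Exclude readings after explant or after non-study surgery for IOP control.
- Cross-tabulate these eyes by whether a hypotony TEAE was reported.

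**Add to SAP 16.2** one sentence saying that unscheduled safety IOP enters this table.

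**Add one listing, independent of the first table**, of all study eyes with postoperative shallow or flat chamber, choroidal effusion or hypotony maculopathy, whatever the IOP. Find them from slit-lamp 'Other' entries, fundus findings and adverse event terms, with a look-up table from the medical safety physician, as SAP 8.2 and 10.0 already do for procedures. It must not be limited to eyes below 6 mm Hg, because a shallow chamber can occur without a measured low pressure.

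**Cost.** One table, one listing and one look-up, from data already collected. No new visit, examination, eCRF page or protocol amendment is needed. Hypotony between visits stays unseen.
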